4.6. Other Analyses

4.6.1. Subgroup analyses

Subgroup analyses of the primary endpoint will be further investigated across the CAT score at baseline:

- Moderate impact [CAT 10-20],
- Severe impact [CAT 21-30],
- Very severe impact [31-40].

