As high symptom burden is one of the key unmet medical needs for COPD patients even among those under the treatment of maintenance therapies, the main goal of this single-armed study is to collect the real-life effectiveness data focusing on symptoms of COPD in patients treated with Trelegy for 12 weeks, by comparison to baseline data which can reflect the benefits of patients who remain symptomatic with their prior maintenance treatment and switch to Trelegy under the discretion of their physicians. Based on previous results [[Marth, 2021](#); [Bansal, 2021](#)], a decrease over 2 unit [minimum clinical meaningful difference (MCID)] of COPD Assessment Test (CAT) score and MCID change (over 100 ml) of forced expiratory volume in one second (FEV1) were observed

for triple therapy after 12-week treatment. Therefore, a 12-week duration is considered to be enough to observe a clinical meaningful change from baseline of the study outcomes, i.e., CAT and FEV₁.

The CAT score is defined as primary outcome because it is recommended by guideline [GOLD, 2021] as the tool for assessment of disease severity and usually leveraged by physicians in daily practice to evaluate the patient's response to treatment. A decrease of 2 unit compared to baseline is considered as the MCID [Kon, 2014]. Other outcomes including lung function and dyspnea can provide data from different dimensions on effectiveness which are also clinically relevant to the evaluation of the response of patients to treatment.

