3.2. Data Source / Data Collection

The investigators will enroll participants by assessing the inclusion/exclusion criteria. The patients will be enrolled at visit 1 and will be followed up prospectively for 12 weeks.

During this trial the following information and measurements will be collected, and the details are listed in [Table 1](#):

To be completed at Visit 1:

- Patient demographics (including sex, age, height, weight)
- Patient past medical history and co-morbid diseases
- Patient smoking history [never a smoker, former smoker (previously smoked ≥ 10 pack year and has not smoked for at least 6 months prior to Visit 1), current smoker (10 pack year and smoked within 6 months prior to Visit 1); the number of pack years for former smoker and current smoker should be calculated (round up to the nearest integer)]
- Patient concomitant medication
- Pregnancy status
- Oxygen saturation
- Patient vital signs and Electrocardiogram (ECG)
- CAT score
- mMRC
- Pulmonary function test (spirometry): pre-dose FEV1, FVC, FEF₂₅₋₇₅ and IC
- Trelegy related AEs
- AEs that lead to the discontinuation of Trelegy
- SAEs

To be completed at Visit 2:

- Patient concomitant medication
- Pregnancy status
- Number of doses of Trelegy taken
- CAT score
- Trelegy related AEs
- AEs that lead to the discontinuation of Trelegy
- SAEs

To be completed at Visit 3 or E.D.:

- Patient concomitant medication
- Pregnancy status
- Number of doses of Trelegy taken
- Patient vital signs
- CAT score
- mMRC
- Pulmonary function test (spirometry): Pre-dosed FEV₁, FVC, FEF₂₅₋₇₅ and IC
- Trelegy related AEs
- AEs that lead to the discontinuation of Trelegy
- SAEs

Table 1 Visit flow chart and data collection schedule

Procedure	Conse nting	Treatment and Observation Period (Days)			E.D.	Notes E.D. = early discontinuation / withdrawal (within 7 days of study discontinuation)
Study visit	V0 ¹ Pre- Scree ning	V1 Screen, enroll & baseline (Day 1)	V2 (Day 28)	V3 End of Study (Day 84)		
Time Window Allowed (days)			±7	±10		
Informed consent ²	X					
Inclusion / exclusion criteria		X				
Demography		X				
Full physical examination including height and weight		X				
Smoking History		X				

Procedure	Conse nting	Treatment and Observation Period (Days)				Notes E.D. = early discontinuation / withdrawal (within 7 days of study discontinuation)
Medical history: past and current medical conditions		X				
Vital signs		X		X	X	
Oxygen saturation		X				
ECG		X				

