3.7 Sample Size Calculations

3.7.1 Statistical assumptions

INTREPID study [study 206854 China CSR GSK Document Number [2019N418769_00](#)] showed that in the real world setting 19% participants had early withdrawn from the Trelegy treatment prior to week 24. Considering the difference in the China clinical practice and study designs, it is assumed that 79% enrolled participants would complete 12 weeks of Trelegy treatment with no intercurrent events, 20% would have the intercurrent event of receiving a new COPD maintenance therapy, 1% would have the intercurrent event of treatment discontinuation.

Based on results from a few studies, i.e., IMPACT [[Lipson](#), 2018; study CTT116855 China CSR GSK Document Number [2018N356723_00](#)], INTREPID [study 206854 China CSR GSK Document Number [2019N418769_00](#)] and one randomized controlled trial (RCT) [[Bansal](#), 2021], it is assumed that a decrease of 2 in the primary endpoint at week 12 will be observed in this study with a common standard deviation of 7 ([Table 2](#)).

Table 2 Assumptions for the primary endpoint

Proportion of each type of participants	Primary endpoint		
	Mean	Standard deviation	
Participants with no intercurrent events	79%	-2	7
Participants receiving other COPD maintenance therapy	20%	-2	7
Participants with treatment discontinuation	1%	0	7
Total	100%	-1.98	7.003

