3.7.3 Sensitivity assessments

The half-width of confidence interval are assessed when the sample size varies under different missingness scenarios ([Table 3](#)). Scenario 1 is the ideal situation where no missingness occurs, which results a half-width of 0.64 for the 95% confidence interval for the inverse probability weighted mean of the primary endpoint with the sample size of 460. Scenario 2 represents a situation with the moderate missingness, which results a

half-width of 0.69 for the 95% confidence interval of the primary endpoint with the sample size of 460. Scenario 3 represents the worst missingness situation, which results a half-width of 0.73 for the 95% confidence interval of the primary endpoint with the sample size of 460.

Table 3 Sample size versus the half-width of the 95% CI for the primary endpoint

Sample size	Data availability status	Proportion of missing data at week 12			Expected inverse probability weighted mean	Half width of 95% CI
		Participants with no intercurrent events	Participants receiving other COPD maintenance therapy	Participants with treatment discontinuation		
280	Scenario 1	No missing	No missing	No missing	-1.98	0.82
	Scenario 2	5% missing	30% missing	50% missing	-1.98	0.87
	Scenario 3	10% missing	50% missing	70% missing	-1.98	0.94
340	Scenario 1	No missing	No missing	No missing	-1.98	0.74
	Scenario 2	5% missing	30% missing	50% missing	-1.98	0.79
	Scenario 3	10% missing	50% missing	70% missing	-1.98	0.85
400	Scenario 1	No missing	No missing	No missing	-1.98	0.69
	Scenario 2	5% missing	30% missing	50% missing	-1.98	0.73
	Scenario 3	10% missing	50% missing	70% missing	-1.98	0.78
460	Scenario 1	No missing	No missing	No missing	-1.98	0.64
	Scenario 2	5% missing	30% missing	50% missing	-1.98	0.69
	Scenario 3	10% missing	50% missing	70% missing	-1.98	0.73

With the planned sample size of 460, the half-width of the 95% confidence interval for the inverse probability weighted mean for the primary endpoint is also assessed when the standard deviation varies (Table 4).

Table 4 The half-width of the 95% CI versus standard deviations when N=460

Standard deviation	Data availability status	Proportion of missing data at week 12			Expected inverse probability weighted mean	Half width of 95% CI
		Participants with no intercurrent events	Participants receiving other COPD maintenance therapy	Participants with treatment discontinuation		
6.5	Scenario 1	No missing	No missing	No missing	-1.98	0.60

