1.2. Study Design

Overview of Study Design and Key Features	
Design Features	
This is a 12-week, prospective, open label, single cohort study. The enrolled participants will be those who are symptomatic under COPD maintenance treatments, and newly prescribed with Trelegy under the discretion by clinical physicians.
 
The study applies a single cohort design to evaluate the effectiveness following 12-week treatment with Trelegy by comparison to baseline data, which can reflect the benefits (i.e., CAT score and FEV1, etc.) of patients who remain symptomatic with their prior maintenance treatment. The decision to prescribe Trelegy shall be independent to the study with medical records providing documentation of a Trelegy prescription.
 
The prospective data collection starts from Visit 1 when Trelegy is taken by patients for the first dose. The participants will complete the CAT score at Visit 1, Visit 2 and Visit 3 or early discontinuation/withdrawal visit (E.D.), and the mMRC at Visit 1 and Visit 3 or E.D. The participants' pulmonary function test will be assessed at Visit 1 and Visit 3 or E.D.. The investigators will record Trelegy-related adverse events (AEs), serious adverse events (SAEs) and AEs that lead to withdrawal from Trelegy.

Study Treatment	All patients will receive Trelegy (FF/UME/CVI ELLIPTA 100/62.5/25 µg) according to the local SmPC. Participants are expected to inhale one dose in the morning from the Trelegy Ellipta at approximately the same time each day for 12 weeks after enrolment.

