4.1.2. Baseline Definition

For all endpoints, the baseline value will be the latest pre-dose of Trelegy assessment with a non-missing value, including those from unscheduled visits. If time is not collected, Day 1 assessments are assumed to be taken prior to first dose and used as baseline, and values at scheduled visit have higher priority than the ones at the unscheduled visits if the two records are on the same day.

Unless otherwise stated, if baseline data is missing, no derivation and/or imputation will be performed and baseline will be set as missing.

All baseline values will be referred to as 'Baseline' in the summary outputs.

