4.2.2. Main analytical approach

Primary analysis will be conducted using an inverse-probability weighted mixed model for repeated measures (MMRM) for the change from baseline in CAT score under the missing at random (MAR) assumption to handle missingness which may occur during the data collection.

The inverse probability weighting (IPW) method can reduce the selection bias caused by the missingness, by weighting the participants whose change from baseline of CAT score is observed at week 12 using the inverse probability of completeness in the endpoint. The key assumption for the IPW method is MAR which means that the missingness mechanism of the primary endpoint could be modelled using the observed factors, i.e. the baseline covariates and the post-baseline covariates by the time of missingness, and no unmeasured confounders are involved in the missingness mechanism.

To estimate the probability of the completeness of the primary endpoint, a logistic model is constructed to model its missingness mechanism with the missingness status as the dependent variable (status=observed, status=missing as the reference group). The following baseline and post-baseline covariates will be considered for the missingness of change from baseline in CAT score at week 12:

- Age,
- Gender,
- Years of COPD,
- Smoking history: smoking status and number of pack years,
- Pre-dose FEV1 at baseline,
- COPD maintenance treatment at baseline,
- CAT score at baseline,
- The change from baseline in CAT score at week 4,
- Intercurrent event status: no intercurrent events, received other COPD maintenance therapy, Trelegy discontinued due to other reason.
The subjects receiving other COPD maintenance therapy are those who have discontinued their Trelegy therapy and switched to other COPD maintenance therapy.
- Duration of Trelegy

The right tail of estimated weights may be truncated by its appropriate percentile if deemed necessary.

The change from baseline in CAT score will be analysed using the MMRM model with the covariates of smoking status, CAT score at baseline, visit, the interaction of CAT score at baseline*visit, in which each observation is weighted with the inverse probabilities derived from the above logistic regression models.

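### Does tabulating change in CAT by bands of the same baseline CAT (SAP 4.6.1) need a change to the plan, given regression to the mean?

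*SAP*

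**What the plan says.** SAP 4.6.1 and Protocol 3.8.2.1 give one sentence, "Subgroup analyses of the primary endpoint will be further investigated across the CAT score at baseline", and three bands: moderate (10-20), severe (21-30) and very severe (31-40).

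The primary endpoint is change in CAT from baseline to week 12. Under SAP 4.1.2, "the baseline value will be the latest pre-dose of Trelegy assessment with a non-missing value". Protocol 3.6.1.1 schedules CAT at Visits 1, 2 and 3/E.D. only, and Table 1 of Protocol 3.2 labels the first of these "V1 Screen, enroll & baseline (Day 1". Protocol 3.4.1 requires CAT of at least 10. One score thus normally serves for eligibility, baseline and band. An unscheduled pre-dose score could become the baseline, but it too would be used twice.

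Under SAP 4.2.2 the change is "analysed using the MMRM model with the covariates of smoking status, CAT score at baseline, visit" and the interaction of baseline CAT with visit, with inverse-probability weights. SAP 4.3.1 and 4.4 call their analyses analogous to the primary one. SAP 4.6.1 does not say this. SAP 2 states that there are no formal hypothesis or significance tests.

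**The concern.** Chance variation in the baseline score enters the band and, with opposite sign, the change. A patient who happens to score high that day is placed in a higher band and is also expected to fall back. Without a control arm or a second scheduled pre-treatment reading, the study cannot remove this effect. A table in which more severe patients improve more could then be taken as evidence of greater effectiveness in severe disease.

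The artefact may exceed the study's own benchmark: "A decrease of 2 unit compared to baseline is considered as the MCID". SAP 4.6.1 also does not say whether the model is fitted within each band or with a band term, nor at which baseline CAT the band means are evaluated. That last choice can make the gradient appear or vanish. Neither document mentions regression to the mean.

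**Working it through.** **1. The plan's own precision figure.** Protocol 3.7.1 assumes "a common standard deviation of 7" (7.003 for the mixture in Table 2) and shares of 79%, 20% and 1%. Table 3, Scenario 3, has 10%, 50% and 70% missing in those groups. The variance of a weighted mean is inflated by the sum of share/(1 - missing):

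- 0.79/0.9 + 0.20/0.5 + 0.01/0.3 = 1.311
- effective n = 460/1.311 = 351
- half-width = 1.96 x 7.003/sqrt(351) = 0.73

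This agrees with Protocol 3.7.3: "Scenario 3 represents the worst missingness situation, which results a half-width of 0.73 for the 95% confidence interval". Scenario 1 gives 1.96 x 7.003/sqrt(460) = 0.64, also as stated. These figures are for the whole cohort. The documents give none for the bands.

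**2. Expected gradient with zero effect.** With equal mean and SD at both visits and correlation r, the expected change at baseline x is -(1 - r)(x - mean). The gap between two bands is therefore (1 - r) times the difference in their mean baseline CAT.

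The documents give no baseline mean, SD or correlation. Assumptions: normal scores with mean 16 to 20 and SD 7 to 8 before selection, rounded, limited to 0-40 and kept if at least 10. At mean 18 and SD 7, simulated mean baselines are 15.6 (band 10-20) and 24.4 (band 21-30), a difference of 8.8.

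| r | (1 - r) x 8.8 | simulated gap, whole grid |
|---|---|---|
| 0.9 | 0.9 | 0.9 |
| 0.8 | 1.8 | 1.8-1.9 |
| 0.7 | 2.6 | 2.6-2.8 |
| 0.6 | 3.5 | 3.5-3.7 |
| 0.5 | 4.4 | 4.4-4.7 |
| 0.4 | 5.3 | 5.2-5.6 |

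The artefact is below the 2-unit MCID at r of 0.8 or more and above it at 0.7 or less. In this grid a planned SD of change of 7 corresponds to r of roughly 0.4 to 0.6 if all the variation is noise. If part of that SD is real variation in response (SD 5 assumed), r is 0.73 to 0.80 and the gap is 2.0 to 2.5.

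The 31-40 band holds about 11 to 48 of 460 patients. With 20 patients and SD 7, its half-width is 1.96 x 7/sqrt(20) = 3.07.

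**3. Effect of the evaluation point.** Mean 18, SD 7, r 0.5, zero effect:

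- Each band at its own mean baseline: +1.2 / -3.2 / -7.6, the same as the raw means.
- A line in baseline CAT fitted within each band and evaluated at the overall mean of 19.5: -0.77 / -0.75 / -0.81.

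The common value of about -0.75 is (1 - 0.5) x (18 - 19.5), the effect of the CAT cut at 10. It is the same in every band, so it adds nothing to the gradient.

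Evaluating at the overall mean does not isolate benefit by severity. At mean 18, SD 7.5 and r 0.8, a true extra benefit of 0.2 per baseline unit implies a true gap of 0.2 x (24.5 - 15.5) = 1.8. At the overall mean the two lower bands then show -0.73 and -0.71, so the true gap disappears as well.

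**4. Would a printed reference help?** A row giving (1 - r) times the baseline difference for r from 0.4 to 0.9 would run from 0.9 to 5.6 points for 21-30. Nearly any plausible gradient lies inside that range, and no r can be taken from the study, because Visits 2 and 3 are both on treatment. With skewed true scores the formula is too large by 0.5 to 2.1 points for 31-40, the band with the fewest patients.

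**The case for a change.** The best argument for a change is that an unstated choice moves the table from a gradient of about 9 points, lowest to highest band, to almost none, and that one sentence would settle it. The band labels invite a severity reading, and SAP 1.2 speaks of change measured "by comparison to baseline data, which can reflect the benefits (i.e., CAT score and FEV1, etc.) of patients who remain symptomatic". Protocol 4 says only in general that the lack of a control group makes results hard to interpret. Band means can also coincide under different truths. At mean 18 and SD 7.5, zero effect with r 0.6 gives +1.01 / -2.60 / -6.26, and a true extra benefit of 0.2 per unit with r 0.8 gives +1.01 / -2.60 / -6.21.

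The mechanism, its direction and the two open choices stand. The rest is weaker. The SAP 1.2 sentence is about the whole cohort against baseline, not about bands. The two coinciding cases differ in SD of change (6.5 against 5.1), and SAP 4.1.1 reports SDs, so the planned summaries are not identical, although the SD alone would not tell a reader which case holds. Subgroup analyses of the primary endpoint are naturally read as the SAP 4.2.2 model by band, so what remains open is narrow. Neither evaluation point would turn the table into evidence of benefit by severity, so fixing one in advance protects no conclusion. A caution sentence would guard against a claim that the plan does not make.

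**Conclusion.** No change is needed. Regression to the mean is expected to produce larger falls in higher baseline CAT bands: about 0.9 to 5.6 points for 21-30 against 10-20, over assumed correlations of 0.9 to 0.4, baseline mean 16 to 20, SD 7 to 8 and zero effect. The direction needs only a correlation below 1 and similar spread at both visits. The size rests wholly on those assumptions and lies on both sides of the 2-unit MCID.

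This limits what a descriptive table in a single-arm study can show. It is not an error in a planned analysis: no test, contrast or claim depends on the bands. An analyst will apply the weighted MMRM, choose how to fit it by band and where to evaluate the means, and footnote both. A writer of the study report who knows that the band and the change share one score will not present the gradient as greater benefit. Stating this in the SAP would be harmless but optional, and reference values would add a range too wide to use.

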4.6.2. Other variables and/or parameters

Not applicable.

4.7. Sequence of Planned Analyses

To support the license renewal, an additional analysis may be performed with the early available study data (i.e. the data in participants who are enrolled by 29 May 2023 and at the time when they all have completed the study or withdrawn from study). This analysis is exclusively for the license renewal purpose and will not have any impact on the study design and other study criteria.

The whole study data will be analysed when all the participants have completed the study or withdrawn from study.

4.8. Changes to Protocol Defined Analyses

Protocol defined that sensitivity analysis will be conducted using the arithmetic mean and missing data will be imputed using multiple imputation under missing at random assumption. The change is that sensitivity analysis will employ a mixed model for repeated measures (MMRM) to estimate the treatment effect. By employing the MMRM model, although the estimate of mean will not change, its standard error may be reduced due to the information from covariates, and the MMRM model provides additional insight to the impact of covariates.

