Sensitivity analysis will be conducted using the arithmetic mean. Missing data will be imputed using multiple imputation under missing at random assumption, for participants with no intercurrent events, receiving other COPD maintenance therapy, with treatment discontinuation, separately if data permits, otherwise may be imputed for the pooled groups.

Subgroup analyses of the primary endpoint will be further investigated across the CAT score at baseline: moderate impact [CAT 10-20], severe impact [CAT 21-30], very severe impact [31-40].

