2. STATISTICAL HYPOTHESES

The primary objective of this study is to evaluate the effectiveness following 12-week treatment with Trelegy by comparison to baseline data. There are no formal hypothesis tests associated with this objective and no formal significance tests.

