4. STATISTICAL ANALYSES

4.1. General Considerations

4.1.1. General Methodology

Unless otherwise specified, continuous data will be summarized using descriptive statistics: n, mean, standard deviation (std), median, minimum and maximum. Categorical data will be summarized as the number and percentage of participants in each category.

Confidence intervals will use 95% confidence levels unless otherwise specified.

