4.2. Primary Endpoint Analyses

4.2.1. Definition of estimand

The primary clinical question of interest is: what is the change from baseline in CAT score at week 12, regardless of receiving a new COPD maintenance therapy or treatment discontinuation.

The estimand is described by the following attributes:

- Population: Symptomatic Chinese COPD participants who are receiving COPD maintenance treatment
- Treatment condition: Trelegy (FF/UME/CVI ELLIPTA 100/62.5/25 µg) one dose daily, inhaled
- Variable: change from baseline of CAT score at week 12.
- Intercurrent events:
 - Receiving other COPD maintenance therapy is addressed by the treatment policy strategy.
 - Treatment discontinuation due to any reason is addressed by the treatment policy strategy.
- Summary measure: average change from baseline in CAT score at week 12.

Rationale: Interest lies in the treatment effect at week 12 in the real-world setting, maybe confounded by other COPD maintenance therapies or the event of treatment discontinuation due to any reason. Therefore, treatment policy strategy is employed to handle the intercurrent events of receiving a new COPD maintenance therapy and treatment discontinuation due to any reason as it reflects the clinical practice.

The COPD Assessment Test (CAT) is a validated 8-item questionnaire developed for use in routine clinical practice to measure the health status of patients with COPD [Jones, 2009; Jones, 2012]. Participants rate their experience on a 6-point scale (Protocol Appendix 1-1), ranging from 0 (no impairment) to 5 (maximum impairment) with a scoring range of 0-40. Higher scores indicated greater disease impact.

In the derivation of CAT total score, the score of an item at a visit is set as the average of the other non-missing items when only this item is missing at that visit.

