If a covariate is with missing values, the missing values in the covariate may be imputed if deemed necessary using appropriate imputation models with information by the time of its missingness. If any imputed covariate is used, the multiple imputation process will be employed to ensure the variability in the missingness of covariates are considered. At least 1000 datasets will be generated which include both observed and imputed values for the covariates. The inverse-probability weighted MMRM estimates, the corresponding standard errors and 95% confidence intervals from each dataset will be combined using the Rubin's rule.

Descriptive statistics will be summarized using the observed data.

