4.2.3. Sensitivity analyses

Sensitivity analysis will be conducted using a MMRM with the covariates of smoking status, CAT score at baseline, visit, the interaction of CAT score at baseline*visit to derive the point estimate and the standard error of change from the baseline in the CAT score, but in which the

missing data in the primary endpoint will be imputed using monotone linear regression multiple imputation under missing at random assumption, for participants with no intercurrent events, receiving other COPD maintenance therapy, with treatment discontinuation, separately if data permits, otherwise may be imputed for the pooled groups, using the observed factors, i.e. the baseline covariates and the post-baseline covariates by the time of missingness.

The missing values in the covariate may be imputed with information by time of its missingness if deemed necessary.

At least 1000 datasets will be generated which include both observed and imputed values for the covariates. The MMRM estimates for the primary endpoint as well as the corresponding standard errors from each complete dataset will be combined using the Rubin's rule.

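### SAP 4.8 claims a smaller standard error for an unchanged mean in the imputed-data sensitivity analysis; in a single cohort that is not a real gain in precision

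*SAP*

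**What the plan says.** Protocol 3.8.2.1 sets the sensitivity analysis of the primary endpoint as multiple imputation under missing at random, followed by a simple average: "Sensitivity analysis will be conducted using the arithmetic mean".

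SAP 4.2.3 keeps the imputation but fits an MMRM to every imputed dataset, with smoking status, baseline CAT, visit and baseline CAT by visit. The estimates and the "corresponding standard errors from each complete dataset will be combined" by Rubin's rule. SAP 4.8 records this as a change from the protocol and gives two reasons. One is that "although the estimate of mean will not change, its standard error may be reduced due to the information from covariates". The other is insight into the covariates.

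The target is in SAP 4.2.1: symptomatic Chinese COPD participants on maintenance treatment, with "Summary measure: average change from baseline in CAT score at week 12". On inference, SAP 2 says "There are no formal hypothesis tests associated with this objective and no formal significance tests", and SAP 4.1.1 says "Confidence intervals will use 95% confidence levels unless otherwise specified".

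Neither document says at which covariate values the week-12 mean is read from the model, or how its standard error is computed.

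**The concern.** If the estimate is the same number in every dataset, it is the same estimator and has one sampling variance. A smaller printed standard error then means that a component of variance has been left out, not that precision has been gained. Covariate adjustment can sharpen a randomised contrast, but this study has one cohort and one mean. The imputation model already uses the covariates, so refitting them on the completed data adds no information about the population mean.

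At stake is the sensitivity interval. With no hypothesis test, the results will be read through intervals. SAP 4.8 presents a narrower one as an advantage over the protocol's method. A reader who compares it with the primary interval, or with the planned half-widths, could credit precision that does not exist.

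**Working it through.** **Inputs from the documents.** N = 460 (Protocol 3.7.2). Mean −1.98, SD 7.003 and intercurrent-event shares 79/20/1% (Protocol 3.7.1, Table 2). Scenario 3 missingness 10/50/70% (Protocol 3.7.3, Table 3). 95% level (SAP 4.1.1).

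**Assumed.** R², the share of the variance of the week-12 change explained by baseline CAT and smoking status, is not in the documents. I take 0.05, 0.15 and 0.25.

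**Step 1: the plan's own half-widths.** With p the event shares and m the missing proportions, half-width = 1.96 × 7.003 × √[Σ p/(1−m) / 460].
- Scenario 1: Σ = 1, giving 0.640.
- Scenario 2: Σ = 0.832 + 0.286 + 0.020 = 1.137, giving 0.683.
- Scenario 3: Σ = 0.878 + 0.400 + 0.033 = 1.311, giving 0.733.

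Table 3 prints 0.64, 0.69 and 0.73, so the figures are reproduced to within 0.01. They use the full, unadjusted SD.

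**Step 2: same estimator.** The model has an intercept for each visit. Its estimating equations therefore force the week-12 residuals to sum to zero when week 12 is complete, as it is after imputation. The fitted week-12 mean at the sample's own covariate means is then the arithmetic mean. In simulated fits of the SAP 4.2.3 model the two differed by less than 5×10⁻¹³. Equality also held when some week-4 values were left missing.

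**Step 3: where the smaller standard error comes from.** The variance of the mean splits as σ²/N = σ²(1−R²)/N + σ²R²/N. The second term is the sampling variation of the covariates. A default least-squares-mean standard error reports only the first.

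At R² = 0.25: 49.04 × 0.75/460 = 0.0800, so the half-width is 1.96 × √0.0800 = 0.554. Adding 49.04 × 0.25/460 = 0.0267 gives 0.1066 and a half-width of 0.640 again. With complete data, coverage of the default interval is 2Φ(1.96√(1−R²)) − 1:

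| R² | Default half-width | Needed | Coverage |
|---|---|---|---|
| 0 | 0.640 | 0.640 | 95.0% |
| 0.05 | 0.624 | 0.640 | 94.4% |
| 0.15 | 0.590 | 0.640 | 92.9% |
| 0.25 | 0.554 | 0.640 | 91.0% |

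An ordinary sandwich standard error does not repair this. In a complete-data ANCOVA simulation at R² = 0.20 it averaged 0.291 against a true 0.325, with 92.0% coverage.

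**Step 4: after multiple imputation, Scenario 3.** This is the setting that SAP 4.8 changes. The simulation assumed baseline CAT truncated normal on 10–40, 35% current smokers, week-4 to week-12 residual correlation 0.6 and week 4 complete. It used 50 imputations (the SAP asks for at least 1000) and 6,000 trials per R², with Monte Carlo error about 0.3 points. Where two values appear, the second is from a separate run at the same N and SD.

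| R² | Default MMRM half-width | Arithmetic-mean half-width | Default coverage | Arithmetic-mean coverage |
|---|---|---|---|---|
| 0.05 | 0.70 / 0.69 | 0.71 / 0.71 | 94.9 / 94.7% | 95.3% |
| 0.15 | 0.66 / 0.66 | 0.70 / 0.70 | 93.6 / 93.9% | 95.2% |
| 0.25 | 0.62 / 0.62 | 0.70 / 0.69 | 92.3 / 92.4% | 95.3% |

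Adding the covariate-sampling term in each dataset before pooling gives half-widths 0.71/0.71/0.70 and coverage 95.4/95.2/95.3%. A hand check at R² = 0.25: √(0.62² + 1.96² × 0.0267) = √(0.384 + 0.102) = 0.70.

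**Step 5: other margins.** If the two smoking levels are weighted equally and 35% are current smokers (assumed), the week-12 mean moves by (0.50 − 0.35) × 1 = 0.15 per 1-point smoking effect. The statement that the mean does not change then fails.

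**The case against.** Several points on the other side are fair.

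- **The SAP does not prescribe a wrong interval.** SAP 4.8 says only that the standard error may fall, and no standard-error method is named. A reader might infer that the SAP commits to an interval that undercovers. It does not: the undercoverage follows from default software output at observed margins. What is wrong as written is the reason given.
- **Not every default is narrower.** With equal smoking weights the standard error can exceed that of the arithmetic mean (factor √(0.25/0.2 + 0.25/0.8) = 1.25 at a 20/80 split, before adjustment for baseline CAT). But the estimate is then a different one, which defeats the other half of the sentence.
- **The effect is small.** R² is assumed. At 0.05 coverage is practically nominal, and 0.08 points is little beside the 2-unit MCID in Protocol 3.6.1.1. The larger shortfalls in Step 3 are for complete data and should not be quoted for the imputed analysis.
- **Absolute coverage depends on the set-up.** A smaller Scenario 3 simulation (R² 0.20, 15 imputations, 1,500 trials) gave 91.3% for the default and 93.3% for the arithmetic mean. The roughly 2-point difference is stable; the levels are less so.
- **The MMRM has other support.** SAP 4.8 also cites covariate insight, and the SAP version history ties the change to the new primary method. Both stand without a precision argument.

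One defence fails. The smaller standard error would be right for a mean conditional on the sampled baseline values, but SAP 4.2.1 defines a population mean.

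**Conclusion.** The precision reason in SAP 4.8 is wrong as written. For the population mean in SAP 4.2.1, the week-12 MMRM mean on completed data at observed margins has exactly the sampling variance of the arithmetic mean. That part is algebra and needs no assumption about R².

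The consequence is conditional and modest. It requires that a default standard error is pooled and that baseline CAT or smoking predicts the change. At R² = 0 there is no effect.

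Two wider readings are not supported. A reader might infer that the planned precision leans on the claimed reduction; it does not, because Protocol 3.7 and SAP 5 use the unadjusted SD of 7. A reader might also infer that the primary interval is shown to be too narrow. SAP 4.8 makes no claim about the primary analysis. That analysis is "analysed using the MMRM model with the covariates of smoking status, CAT score at baseline, visit" and weighted, so its variance method deserves a check for the same omission, but its weights raise separate issues and I rely on no figure for it.

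**What to change.** 1. In SAP 4.8, delete the clause that the standard error may be reduced. The covariate-insight reason can stay.
2. In SAP 4.2.3, state that the week-12 mean is evaluated at the FAS mean baseline CAT and the FAS smoking distribution.
3. In SAP 4.2.3, choose one of two standard errors:
   - keep the protocol's arithmetic mean with its own standard error under Rubin's rule; or
   - keep the MMRM and, in each imputed dataset, add the variance of the fitted week-12 values over the FAS, divided by N, to the model variance before pooling.
4. When naming the variance method for the primary analysis in SAP 4.2.2, check whether it includes covariate sampling.

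Items 1 to 3 cost SAP wording and at most one variance term in the program. The sensitivity interval becomes slightly wider (about 0.70–0.71 in Scenario 3 under the assumptions above), and the apparent precision gain is given up. No data collection or sample-size change is needed.
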